5.3.3.8 Dermatology Life Quality Index

The DLQI is a 10-item questionnaire with each item scored from 0 to 3. Further information on the scoring of the DLQI is provided in [Section 18](#).

The DLQI score is the sum of the 10 individual items.

During the course of the study it was found that question 7 of the DLQI had been asked incorrectly. Therefore the following action will be taken: DLQI questionnaires of all participants at all visits (including Baseline) will be assigned a score of 0 for question 7. This concurs with the questionnaire's instructions on how to handle a question with a missing response. Up to one question can have a missing response and the total DLQI score is still considered valid. In the event that any questionnaire contains a missing response to another question, the DLQI score will be set to missing.

Once the error was found it was decided not to correct the asking of the question going forward, since this would result in comparing a slightly different questionnaire at baseline to later time points for the majority of participants and therefore complicate interpretation of change from baseline.

In order to investigate any potential effect of this error on conclusions drawn, sensitivity analyses of the DLQI will be carried out using the following scoring for question 7, based on the first part of the question:

Answer to first part of question 7	Score assigned
Yes	3
No	1.5 (median of the possible scores 0, 1, 2 and 3)
Not relevant	0

The second part of the question will not be used as this was where the error occurred.

5.3.3.9 Modified Nail Psoriasis Severity Index

The mNAPSI will only be collected in participants with psoriatic nail involvement.

The mNAPSI is assessed for each of the participant's 10 fingernails as detailed in [Section 19](#). The mNAPSI score is the sum of the 10 scores for the individual nails.

If the investigator indicates at a visit that there is no nail disease, a score of zero will be assigned.

5.3.3.10 Psoriasis Symptom Inventory

The PSI will be completed daily by participants for the 7 days prior to each visit as detailed in [Section 20](#).

For each of the 8 symptoms, the daily scores will be averaged to give a weekly symptom score for that visit. Data must be provided for at least 5 of the 7 days prior to the visit for a weekly symptom score to be calculated.

The PSI total score at the visit will be the sum of the 8 weekly symptom scores.

5.3.3.11 SF-36 Bodily Pain and Vitality Scores

The SF-36 bodily pain and vitality scores will be calculated using the algorithms provided by the RAND corporation as detailed in [Section 21](#).

The SF-36 bodily pain score will be the average of the two question scores for pain and will be calculated if at least one of the two questions have been answered.

The SF-36 vitality score will be the average of the four question scores for vitality/energy and will be calculated if at least two of the two questions have been answered.

5.3.3.12 Pain and Fatigue Visual Analogue Scales

The pain VAS will ask the question: How severe is your pain today?

Participants will score this by marking a point on a line which goes from 0=no pain to 100=very severe pain

The fatigue VAS will ask the question: How much of a problem has fatigue or tiredness been for you in the past week?

Participants will score this by marking a point on a line which goes from 0=fatigue is no problem to 100=fatigue is a major problem.

5.3.4 Safety

5.3.4.1 Duration of Exposure

The duration of exposure will be calculated as

$$\text{Duration of exposure (days)} = \text{Treatment stop date} - \text{treatment start date} + 1$$

5.3.4.2 Treatment-Emergent Adverse Events

An adverse event (AE) will be classified as ‘treatment-emergent’ if the onset date/time was on or after the start date/time of study treatment. Where dates or times are missing or partially missing, AEs will be assumed to be treatment-emergent, unless there is clear evidence (through comparison of partial dates/times, see [Section 7.3.1](#)) to suggest that the AE started prior to dosing.

AEs will be classified into the following study phases based on the onset date/time of the AE after any imputations:

- Pre-Treatment Phase: All AEs with onset date/time prior to the first dose of randomized study treatment
- Treatment Phase: All AEs with onset date/time at the time of or after the first dose of randomized study treatment (Day 1) up to and including the date of the last dose of treatment received.
- Follow-up Phase: All AEs with onset date after the date of the last dose of treatment received.

For participants who complete 16 weeks of dosing per protocol the Treatment Phase will be from Day 1 to Day 112 and the Follow-up Phase will be from Day 113 until their last day in the study. In all cases the day will be assumed to start at 00:00 hours and end at 23:59 hours. Adverse events occurring in both the Treatment Phase and Follow-up Phase are classified as treatment emergent.

For the primary analysis which considers only data collected in Part A, only events which start on or prior to the end of Part A date will be included in the adverse event summaries.

The onset phase of all AEs will be included in the relevant data listings.

For the final analysis, only treatment related events which start in Part B will be included in the adverse event summaries.

Only treatment related events which start in Part B and any Part A AEs which change in Part B will be included in the relevant data listings.

6 Sample Size

The sample size of 225 participants in total, has been chosen to explore the tolerability and safety of EDP1815. Although the study will use a model-based probability inference approach in a Bayesian framework, the following power calculation was also performed (using a basic frequentist approach) in order to give confidence that enough participants are available to find a clinically meaningful difference between active dose and placebo if the below assumptions are met.

The primary efficacy endpoint is the percent change from baseline in the PASI score at Week 16. Percent change from baseline relative to placebo will be estimated within the model ([Section 9.4.3](#)) as (percent change in active) - (percent change in placebo), with a negative value indicating a greater improvement for active than placebo. A percent change from baseline relative to placebo of at least 20% will be considered clinically meaningful. The pooled standard deviation across all doses is assumed to be 25%.

Participants in the placebo arm of each cohort will be pooled for the statistical analysis in order to compare active and control arms resulting in 75 participants randomized to the pooled placebo group and 50 participants randomized to each active treatment group (EDP1815 0.8 \times 10¹¹ cells, EDP1815 3.2 \times 10¹¹ cells, and EDP1815 8.0 \times 10¹¹ cells). Assuming that no more than 15% of

participants will discontinue treatment before the Week 16 visit, at least 42 active and 21 placebo participants in each of the 3 cohorts are expected to provide data through the Week 16 visit.

Each pairwise comparison between pooled placebo and active dose would be expected to have more than 95% power to detect a difference between the treatment groups at the 5% significance level under the assumption that pooling the placebo groups is a valid strategy. If the 3 placebo cohorts are considered too heterogeneous for pooling into a single reference group ([Section 9.1](#)), the power to detect a difference in each within-cohort pairwise comparison between active and placebo doses would be greater than 80%.

As the statistical inference for this study will focus on estimation rather than testing a formal hypothesis, no multiplicity adjustments of the different comparisons between groups in order to control the study-wise type I error rate will be performed.

Similarly, as there is no intention to use any interim analyses to stop the study early for efficacy ([Section 7.4](#)), no adjustments for multiplicity will be made to account for any analyses performed as part of the interim analyses.

7 General Considerations

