3.1 Study Design

This is a multicenter, randomized, double-blind, placebo-controlled, parallel-cohort, dose-ranging study of participants with mild to moderate plaque psoriasis (Section 4.1).

Part A of the study comprises a screening period of up to 4 weeks, a baseline visit, a treatment period of 16 weeks (8 planned study site visits), and a follow-up visit at Week 20 (4 weeks after cessation of dosing). Part A of the study therefore comprises a total of 11 scheduled study visits, and on completion of Part A, the primary analysis will be performed.

Part B of the study is designed to assess the durability of treatment response and incidence of rebound of psoriasis following cessation of dosing. All participants will attend for skin assessments at Weeks 24 and 28, unless they have previously experienced treatment failure and/or had rebound of disease. A final visit at Week 40 will also be performed for those participants who experienced treatment response at Week 16 of treatment, but have not yet met the definition of disease relapse. Part B of the study therefore comprises a maximum of 3 additional scheduled study visits with a follow-up of up to 40 weeks (24 weeks after cessation of dosing), and on completion of Part B, the final analysis will be performed.

The study design is presented in Figure 3-1, and the SoA is presented in Table 6-1 for Part A, and in Table 6-2 for Part B.

After eligibility is confirmed during the screening period (Section 4.1), participants will be randomly assigned in a 1:1:1 ratio to 1 of the following 3 parallel cohorts:

- Cohort 1: 0.8×10^{11} cells of EDP1815 or matching placebo administered as 1 PIC, once daily (Section 5.2).
- Cohort 2: 3.2×10^{11} cells of EDP1815 or matching placebo administered as 4 PICs, once daily (Section 5.2).
- Cohort 3: 8.0×10^{11} cells of EDP1815 or matching placebo administered as 10 PICs, once daily (Section 5.2).

In each cohort, approximately 75 participants will be randomly assigned in a 2:1 ratio to receive either EDP1815 or matching placebo once daily for 16 weeks.

[figure not shown]
An interim analysis may be performed after at least 50% of participants have completed at least 12 weeks of treatment (Section 7.6.7).

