6.2 Safety and Tolerability Assessments

6.2.1 Adverse Events

6.2.1.1 Definitions

6.2.1.1.1 Adverse Events

The investigator is responsible for reporting all AEs that are observed or reported during the study, regardless of their relationship to the study drug or their clinical significance.

An AE is defined as any untoward medical occurrence in a participant enrolled into this study regardless of its causal relationship to the study drug. Participants will be instructed to contact the investigator at any time after randomization if any symptoms develop.

A TEAE is defined as any event not present before exposure to the study drug or any event already present that worsens in either intensity or frequency after exposure to the study drug.

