6.2.1.2 Eliciting and Documenting Adverse Events

Adverse events will be reported from the date of signed informed consent and through for 28 days after cessation of dosing. Adverse events occurring after the 28 days post-treatment would only be reported if the investigator considers it to be related to the study treatment.

If the investigator learns of any SAE, including a death, at any time after a participant has been discharged from the study, and he/she considers the event to be reasonably related to the study drug or study participation, the investigator must promptly notify the sponsor (or designee).

Serious AEs that occur more than 30 days after the last dose of study drug need not be reported unless the investigator considers them related to the study drug.

At every study visit, participants will be asked a standard nonleading question to elicit any medically related changes in their well-being. They will also be asked if they have been hospitalized, had any accidents, used any new medications, changed concomitant medication regimens (prescription or OTC medications), noticed any changes in bowel habits, or had unplanned visits to their general practitioner since the last visit.

In addition to participant observations, AEs identified from any study data (eg, laboratory values, physical examination findings, ECG changes) or identified from review of other documents (eg, participant diaries) that are relevant to participant safety will be documented on the AE page in the eCRF.

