6.2.1.2.1 Assessment of Severity

The severity, or intensity, of an AE refers to the extent to which an AE affects the participant's daily activities or their health. The intensity of the AE will be rated in accordance with the CTCAE version 5.0.

Changes in the severity of an AE should be documented to allow an assessment of the duration of the event at each level of intensity to be performed. Adverse events characterized as intermittent do not require documentation of onset and duration of each episode.

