10.2 Adverse Events

Adverse events will be reported from the date of signed informed consent and through for 28 days after cessation of dosing. Adverse events occurring after the 28 days post-treatment would only be reported if the investigator considers it to be related to the study treatment.

Only treatment emergent AEs (TEAEs) will be included in the summaries, pre-treatment AEs will be included in the listings of all AEs.

In the primary analysis at the end of Part A, only adverse events which started on or before date of the end of Part A will be included in the summaries.

In the final analysis at the end of Part B, only adverse events which started during Part B will be included in the summaries. Treatment related events which start in Part B and any Part A AEs which change in Part B will be included in the relevant data listings.

All AEs will be coded using version 23.0 of MedDRA. Severity of event will be coded using the Common Terminology Criteria for Adverse Events v5.0 (CTCAE).

An overview of TEAEs will be produced showing the number and percentage of participants with:

- Any TEAEs (Part A)
- Any TEAE of CTCAE grade 2 or above (Part A)
- Any TEAE of CTCAE grade 3 or above (Part A)
- Any TEAE of CTCAE grade 4 or above (Part A)
- Any fatal TEAE (Part A)
- Any serious TEAE (Part A)
- Any TEAE leading to permanent discontinuation of study drug (Part A)
- Any TEAE leading to withdrawal from the study (Part A)
- Any related TEAE (Part A and Part B)
- Any related TEAE of CTCAE grade 2 or above (Part A and Part B)
- Any related TEAE of CTCAE grade 3 or above (Part A and Part B)
- Any related TEAE of CTCAE grade 4 or above (Part A and Part B)
- Any related fatal TEAE (Part A and Part B)
- Any related serious TEAE (Part A and Part B)
- Any related TEAE leading to permanent discontinuation of study drug (Part A and Part B)
- Any related TEAE leading to withdrawal from the study (Part A and Part B)

Related events are those which were considered by the investigator to be possibly, probably or definitely related to study drug.

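### SAP 5.3.4.2 defines treatment-emergent AEs by onset date alone, omitting the protocol's worsening limb, and Table 8 does not declare the change

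*SAP*

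**What the plan says.** Protocol 6.2.1.1.1 gives two routes to treatment-emergent status. One is an event absent before exposure. The other is "any event already present that worsens in either intensity or frequency after exposure to the study drug".

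SAP 5.3.4.2 has one route: an event is treatment-emergent "if the onset date/time was on or after the start date/time of study treatment". The same section assigns study phases by onset, and its Pre-Treatment Phase is "All AEs with onset date/time prior to the first dose of randomized study treatment".

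SAP 10.2 makes this flag the gate to the tables: "Only treatment emergent AEs (TEAEs) will be included in the summaries, pre-treatment AEs will be included in the listings of all AEs".

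AEs are collected before dosing. Protocol 6.2.1.2 states "Adverse events will be reported from the date of signed informed consent", and Protocol 3.1 allows "a screening period of up to 4 weeks".

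On events that change grade, Protocol 6.2.1.2.1 says: "Changes in the severity of an AE should be documented to allow an assessment of the duration of the event at each level" of intensity.

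SAP Section 13, Table 8, declares four changes from the protocol: the timing of the interim analysis, the DLQI sensitivity analyses, the partial relapse definition and the Part B population. The definition of a treatment-emergent event is not among them.

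**The concern.** The two documents define the same term differently, and the narrower definition is the one that will be programmed. Safety is part of the primary objective (Protocol 2.1, SAP 4.1), and both documents say the sample size was chosen to explore tolerability and safety. If a complaint that began in screening becomes severe, serious or treatment-limiting on study drug, the protocol calls it treatment-emergent, while the SAP may keep it out of every AE table.

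The omission also runs against the SAP's otherwise cautious handling. Events with missing or partial dates are presumed treatment-emergent unless there is clear evidence of an earlier start (5.3.4.2), and a missing causality assessment is counted as related (7.3.2).

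**Working it through.** The plan states no figure on this point and no arithmetic applies. The check is a comparison of text.

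1. **Definitions.** Protocol: new event, or worsening of an existing one in intensity or frequency. SAP: onset on or after the start of treatment. The worsening limb has no counterpart in SAP 5.3.4.2.

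2. **Is the limb restored elsewhere in the SAP?** No. The sentence in 5.3.4.2 that treats Treatment Phase and Follow-up Phase events as emergent does not help, because both phases are set by onset. Section 7.3.1 only imputes partial dates. Sections 10.2 and 10.3 use the flag without redefining it.

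3. **Can affected events arise?** Yes. Reporting starts at consent, and Protocol Table 6-1 places screening between Day -28 and Day -7. Each participant on schedule therefore has at least a week before first dose in which an AE can begin.

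4. **Which onset date does a worsened event carry?** Neither document says outright. Three passages lean towards one record keeping its original onset:
   - Protocol 6.2.1.2.1 wants the duration of an event at each intensity, which describes a single event passing through several grades.
   - The same section does not require onset and duration for each episode of an intermittent AE, so a rise in frequency need not create a new onset date.
   - SAP 5.3.4.2 and 10.2 refer to events from Part A that later change during Part B, and send them to listings.

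5. **Trace one case.** Take an AE that begins after consent and before first dose and rises to Grade 3 on treatment, with its onset date unchanged. Under the protocol it is treatment-emergent. Under the SAP it is Pre-Treatment. All eleven AE tables in SAP 15.3.1 (14.3.1.1.1 to 14.3.1.8) and both AE tables in 15.5.1 are restricted to TEAEs, so the event enters none of them. That includes the related, Grade 3 or above, serious, discontinuation and withdrawal tables. It would appear in listing 16.2.7.1.1. If serious it would also be in 16.2.7.1.2, and if it led to stopping study drug, in 16.2.7.1.4.

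6. **What is not touched.** Laboratory, QTcF and vital-sign shift tables (SAP 10.5, 10.6.1, 10.6.2) compare baseline with the worst post-baseline value and do not use the TEAE flag. SAE reporting (Protocol 6.2.1.3.1) and the halting criteria (Protocol 11.3.1) do not use it either.

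7. **Size.** The documents give no rate for AEs starting in screening and none for their worsening. No count can be derived. A direction can be stated: these events begin before first dose, so randomisation should balance them across arms, but their worsening is a post-randomisation outcome. If study drug aggravates such events, the ones left out are those that would show it.

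**The case against.** The best reply is that the protocol's recording rules may deliver the second limb without help from the SAP. Protocol 6.2.1.3 has a condition present at screening recorded as an AE if it deteriorates more than would be expected. Protocol 6.4 has laboratory, ECG and vital-sign abnormalities that worsen from baseline recorded as AEs, apart from those associated with the underlying disease. If sites date those records at the deterioration, the SAP's onset rule counts them. If sites also open a new record whenever an AE changes grade, the onset rule would capture worsened AEs as well.

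Much of this stands. It narrows the exposed group to AEs that start between consent and first dose and worsen under an unchanged onset date. It does not close the gap: neither document tells sites to open a new record on worsening, and the passages in step 4 lean the other way. An onset rule reproduces the protocol definition only if that convention is written down.

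A reader might infer three stronger things that the documents do not support:
- That worsened screening events disappear from all safety reporting. Only the AE summary tables depend on the flag; the other safety summaries and the listings keep the information.
- That the onset date certainly stays before first dose. This is an inference from wording, not a stated rule.
- That a number of missing participants can be quoted. Any such number would rest on assumed rates. Even then, a worsened event would not be lost from every table: one that stays below Grade 3 belongs in no Grade 3 table, and a participant with another TEAE is still counted in the overall row.

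**Conclusion.** The point holds as an undeclared conflict between SAP 5.3.4.2 and Protocol 6.2.1.1.1 that can undercount TEAEs. Its reach is limited to AE summary tables and to AEs that begin after consent and before first dose. It assumes that a worsening is kept on the original record, which the documents suggest but do not state. The size is unknown. The change should be made because safety is a primary objective and the correction only restores the protocol's own definition.

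**What to change.** Amend SAP 5.3.4.2 so that an AE with onset before first dose is treatment-emergent if its recorded CTCAE grade increases on or after first dose. Date it at the worsening, which also sets its phase, and count it once at the worsened grade. Add a guard against double counting: where the worsening was entered as a new record, the two records count as one event.

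Treat worsening in frequency separately. It cannot be derived from severity-change records, because Protocol 6.2.1.2.1 exempts intermittent AEs from episode-level documentation and Protocol 6.2.1.3 lists no frequency item. Count it where the investigator records it.

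If the onset-only rule is intended, declare and justify it in Table 8 instead.

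The cost is one added derivation and a check, before programming, of how sites record severity changes. No new data collection is needed for the grade limb, since the protocol already asks for those changes to be documented.

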7.1 Analysis Populations

7.1.1 Enrolled Population

The enrolled set will consist of all participants who sign the ICF.

7.1.2 Modified Intention to Treat Population

The modified intention to treat (mITT) population will consist of all participants who were randomised to treatment and who received at least one dose of study treatment. Participants who withdraw from the study before the end of Week 4 and are replaced will be included in this analysis set.

All analyses using the mITT population will group participants according to randomised treatment.

